**Table 2: Study Schedule**

SCHEDULED STUDY PROCEDURE	SCREEN AND ENROLLMENT (VISIT 0)	BASELINE (VISIT 1)	MID INTERVENTION 6 WEEKS (VISIT 2)	FINAL VISIT 12 WEEKS (VISIT 3)
HCP INCLUSION / EXCLUSION	X			
CONSENT TO CONTACT	X			
INFORMED CONSENT	X			
FINAL STUDY ELIGIBILITY	X			
DEMOGRAPHIC DATA		X		
MEDICAL HISTORY		X		
CONCOMITANT MEDICATIONS		X		X
LAB DATA		X		X

PRIMARY FEASIBILITY DATA				
NUMBER APPROACHED				X
NUMBER ELIGIBLE				X
SESSION ATTENDANCE				X
STUDY WITHDRAWAL				X
SECONDARY OUTCOMES				
LEVEL 2 –ANXIETY – ADULT (PROMIS EMOTIONAL DISTRESS – ANXIETY – SHORT FORM)		X	X	X
CONNOR-DAVIDSON RESILIENCE SCALE (2-ITEM)		X	X	X
EDMONTON SYMPTOM ASSESSMENT SYSTEM REVISED (ESAS-r)		X	X	X
NATIONAL COMPREHENSIVE CANCER NETWORK (NCCN) DISTRESS THERMOMETER		X	X	X
PROMIS NEURO-QOL V1.0 POSITIVE AFFECT AND WELL-BEING SHORT FORM		X	X	X
LEVEL 2 – ANGER – ADULT (PROMIS EMOTIONAL DISTRESS – ANGER – SHORT FORM)		X	X	X
PROMIS V1.1– PAIN INTERFERENCE 6a SHORT FORM		X	X	X
LEVEL 2 – SLEEP DISTURBANCE – ADULT (PROMIS SLEEP DISTURBANCE – SHORT FORM)		X	X	X
END OF STUDY PARTICIPANT QUESTIONNAIRE				X

*Focus groups will now occur following the DBT pilot intervention if the intervention demonstrates feasibility, rather than after the above two activities as indicated in previous version of the protocol.*

**3) FOCUS GROUPS : *Collect additional perspectives regarding tailoring of DBT intervention and potential barriers/facilitators to implementation – WILL BE COMPLETED AFTER AIM 3 ONLY IF PILOT DBT INTERVENTION DEMONSTRATES FEASIBILITY***

Focus groups and interviews will help us gain deeper perspective and understanding as to how the DBT intervention should be tailored for people receiving HD with diverse characteristics and help identify potential barriers/facilitators to its implementation. Stakeholders will include healthcare providers, people receiving HD, caregivers, Indigenous consultants, researchers and policy-/decision-makers.

People with advanced kidney disease nearing hemodialysis, those receiving HD and caregivers with direct HD experience will be invited to participate in in-person focus group discussions. In total, we anticipate that 2-3 focus groups involving participants at two sites (Winnipeg and Halifax) will be conducted. We plan to conduct 2 patient/caregiver focus groups in Winnipeg with 6-10 participants per group (minimum total n=12), which is generally considered the optimum size of focus group discussions. However, the number of focus groups will depend on when theoretical saturation is reached; the point when little or no new information informing the research objectives emerge. Due to logistical issues that may influence the number of participants that unexpectedly do not attend the focus groups, up to 12 participants will be scheduled for each focus group to ensure the minimum sample size is reached. In the event that a focus group participant is unable to attend a focus group (due to schedule conflicts, health issues or other reasons) we will invite them to a one-on-one interview in lieu of the focus group.

Participants will be recruited from dialysis units in Winnipeg, including the Seven Oaks Hemodialysis Unit and Health Sciences Centre (Central Dialysis Unit and Sherbrook Centre Hemodialysis Unit). A research team member will contact clinical staff (e.g. nephrologists, nurse managers and nurses from each of the facilities) to provide information about the study and seek to identify potentially eligible study patients. An information poster advertising the focus groups will be posted in the waiting room of Kidney Clinics and HD waiting rooms at both sites. Patients will initially be approached at their usually scheduled hemodialysis session by their bedside nurse who will briefly explain the study to them, provide an information letter, and determine their interest in participating. Patients who express interest will complete a consent to contact form and will then be contacted by a research assistant who will provide further details about the study and determine their willingness to participate in the focus groups. Eligible participants will be currently treated with HD, have initiated HD at least 2 months earlier, be aged 18 years or older, and be able to communicate in English.

To identify approaches and supports needed for culturally-appropriate care, we will seek to recruit 25% of participants in Manitoba from Indigenous (both First Nations and Metis) backgrounds to participate in focus groups and interviews. Following OCAP principles we will seek the wisdom of Indigenous stakeholders, including patients, healthcare workers and Indigenous knowledge keepers. At least one of the Winnipeg

focus groups will focus on the Indigenous perspective and will include Indigenous facilitators and an Indigenous Knowledge Keeper. ***Details of this focus group will be included in a subsequent amendment that will be submitted to ethics after additional consultation with Indigenous communities/organizations in Manitoba to assist with design, content and facilitation.***

When potential participants are contacted, they will be asked whether they have a caregiver who might also be interested in participating. Caregivers may be a family member or significant person in their life who is intimately aware of their illness. Attempts will be made to recruit people receiving dialysis of different genders and ethnicity, from a range of ages, who are originally from both urban and rural settings. Advertisements informing participants and their caregivers of the research opportunity will be posted in the dialysis unit waiting areas, on the CNTN, Can-SOLVE and Kidney Foundation of Canada websites blasts.

People receiving HD and caregivers who are eligible and willing to participate will sign an informed consent form. Focus group participants will be offered \$50 reimbursement to cover their time and transportation costs. Due to the nature of the topic of mental health care, a social worker, mental health counsellor or therapist will be available to debrief with participants after (or if necessary during) each focus group.

Should recruitment for focus groups be difficult due to participants' dialysis or work schedules, inability to travel, and other commitments, individual interviews will be considered as an alternative. The same recruitment procedure, consent, data collection and debriefing procedures would apply in these situations.

The focus groups will be 90-120 minutes in duration and conducted in a location relatively accessible to patients and caregivers. A facilitator will moderate the focus groups, while a co-facilitator will observe and record the contextual details of each discussion. We will use MS teams and its built in transcriber software to record and transcribe focus groups. A question guide with open-ended questions will be developed to explore the topics of interest. An interactive activity will be used to generate ideas as well as a voting exercise to discuss priorities, choices, and reasons for these choices. Poster boards/White boards and sticky notes will be used to facilitate the discussion. The welcome/introductions will be approximately 5-10 minutes while the subsequent focus group discussion will be 60-80 minutes in duration. See focus group discussion guide for more detail. Participants will also complete pre-focus demographic questionnaires. The focus group guide will be pilot tested and refined with project patient partners to ensure clarity of the questions.

In the circumstance where an interested individual cannot attend a focus group, individual semi-structured interviews will occur in lieu of the focus group. Interviews will be 30 to 45 minutes in duration and ideally conducted face-to-face at a location convenient for the participant, but via telephone or video-call if necessary. See interview guide for details. One interviewer will conduct the interviews. All interviews will be audio-recorded and transcribed verbatim using MS Teams platform.

All participants will be asked for their consent to audio record the focus groups discussions and the interviews. Participants will be assured that their identity will be kept confidential by researchers. A consent form approved by the University of Manitoba

Health Research Ethics Board will be completed prior to the commencement of their focus group session or interview.

The same study protocol, including DBT implementation study and focus groups with patients/caregivers will be implemented in Halifax, following ethics approval from Dalhousie University. Ideas and de-identified direct quotes from focus groups and interviews will be used in a combined form for final reports and presentations of the evaluation information. At no time will names of participants be associated with any of the data collected or presented.

### **Data Analysis - Focus Groups/Interviews**

Analysis of focus groups and interview data will be led by two investigators who will:

- 1) Achieve immersion by reading the initial focus group/interview data in its entirety to acquire an overall sense of the data;
- 2) Read the focus group or interview data and highlight words or phrases that capture key concepts, which become the codes;
- 3) Take notes of initial impressions, thoughts, and interpretation;
- 4) Develop codes;
- 5) Sort codes that are related to each other into themes and subthemes.

Investigators will meet together to verify themes and their descriptors for each group of participants. Codes will be generated from the initial focus group and interview data independently and they will be systematically applied to identify themes and patterns for subsequent groups. The process will be reflexive and interactive as continual data collection and data analysis will shape each other. For example, code titles or definitions identified based on the first focus groups may be modified based on data collected during the second, and new codes may be added requiring recoding of the first focus group transcript. An Indigenous research assistant will participate in the analysis of the Indigenous focus group.

Mental health care gaps and potential innovations and solutions will be categorized accordingly. Themes and subthemes will be identified under these overarching categories, including the reasons why strategies have been chosen. Definitions will be developed for existing codes, themes, and subthemes, and exemplars of these will be reported in the findings. Investigators will meet together to verify themes and their descriptors for each group of participants. Themes will be presented to the remaining investigative team, including patient partners for verification.

Data collected from both study sites will be analyzed and reported in aggregate. Quantitative demographic data from the participant questionnaires will be analyzed and reported by frequency to describe our participants. We will review results of any analysis which is concerned with Indigenous community membership with the Can-SOLVE CKD Indigenous Peoples' Engagement and Research Council (IPERC), an Indigenous Elder Knowledge Keeper and Indigenous Patient Partners and Indigenous Research Assistants to help with interpretation of our findings.

### **Risks and Benefits of Study Participation:**

Participants in this study will discuss and be asked about their mental health. Previous work has demonstrated that asking adult research participants about their past experiences in these domains is no more distressing than asking about other personal experiences (e.g. scholastic achievement; body image) and is not typically harmful.

It is possible that some participants will find participating in the survey, PSP, DBT pilots and focus groups therapeutic and/or rewarding. Participants may benefit from improving mental health and building connections with other patients going through similar experiences. Some people may find it meaningful to be part of a research project. The information we learn from the project will benefit society's understanding of the challenges to mental health in people receiving hemodialysis and their solutions.

However, no benefits related to study participation can be guaranteed. DBT participants will be reimbursed for their transportation to in-person DBT group sessions and will share a meal or snack with other group participants. Focus group participants will receive a \$50 honorarium for their time and expenses related to attendance. Additional reimbursement for childcare as needed will be provided as well.

Conversely, it is possible that some participants may experience psychological discomfort while participating in DBT or focus group sessions and/or while answering questions related to study activities. To minimize the possible distress due to answering questions about mental illness, participants will be told during the consent process that they may skip any questions that make them feel uncomfortable and that they are free to discontinue participation at any time without penalty.

Due to the nature of the topic of mental health care, external to research, the kidney care staff (social workers and nephrologists) will manage the well-being of clients through standard clinical care processes. Additionally, we will provide participants with a list of resources available outside of therapy sessions, including the environmental scan of mental health resources available for people receiving hemodialysis in Manitoba, SOGH renal social workers, the elder partnering with the Mind the Gap project and the mental health crisis line to debrief with participants as necessary. Participants who wish to withdraw will also receive a list of mental health resources in Manitoba. At the end of the DBT program, all participants will also receive this list again.

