**Study Setting:**

Two 12-week DBT sessions (one virtual and one in-person) will be provided. The in-person sessions will be held weekly at the Seven Oaks General Hospital Campus in meeting rooms away from the hemodialysis unit. Virtual sessions will be video conferences held using the MS Teams platform.

**Study Population:***Inclusion Criteria:*

- Age  $\geq$  18 years old
- Individuals followed in the Manitoba Kidney Health Program at the SOGH or HSC sites with advanced chronic kidney disease not yet on facility-based hemodialysis but with plans to start within 1 month; OR
- Individuals followed in the Manitoba Kidney Health Program at the SOGH or HSC sites who have initiated facility-based hemodialysis within the last 90 days
- Able and willing to attend weekly DBT sessions (either virtually or in-person)
- Experiencing self-reported psychological distress related to advanced kidney disease or initiation of hemodialysis
- Deemed eligible to participate by study clinical psychologist

*Exclusion Criteria:*

- Unable to complete intervention due to planned relocation/transplant/modality change
- Unable to communicate in English
- Deemed by hemodialysis unit staff/physician/study psychologist to be unable to participate fully in study activities due to:
  - Actively participating in psychiatric care with psychiatric (DSM-5) diagnosis
  - Requiring referral for psychiatric care as per facility-based HD care provider assessment
  - Current psychotic symptoms
  - Cognitive impairment that would limit ability to participate in group or complete homework
  - Safety risk to staff (e.g. physical aggression)
  - Antisocial personality disorder or other issues that may limit ability to constructively participate in peer group
  - Severe comorbid substance use disorder (if present will offer referral to addictions resources or Addictions Psychiatry)

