d. **Emotional Distress** using the self-reported National Comprehensive Cancer Network (NCCN) Distress Thermometer. This single-item measure asks the individual about their distress level experienced in the past 7 days, using a 10-point Likert scale ranging from 0 (no distress) to 10 (extreme distress). Additionally, there is a 39-item problem list used to identify potential sources of distress in individuals, categorized into five domains: physical, practical, social, emotional, and spiritual/religious.

Time for completion: 1-10 minutes.

e. **Well-being** using the PROMIS Neuro-QOL V1.0 Positive Affect and Well-Being Short Form. This 9-item self-reported survey measures positive aspects of mental health and well-being in the past week, using a 5-point Likert scale ranging from 1 (never) to 5 (always). Time for completion: 5 minutes

In addition, participants will complete a questionnaire seeking perspectives on participant experiences with the DBT program at the end of the 12 week DBT program.

f. **End of study participant questionnaire:** The initial version of this 10-item self-reported questionnaire investigating perspectives on participant experiences in the DBT groups will be piloted by study patient partners to ensure readability and face validity and modified accordingly. The survey includes questions that require yes/no and open text answers to provide participants with ample opportunity to provide and explain feedback regarding the DBT program. We will use perspectives shared through this questionnaire to modify the plans for the virtual DBT session and future in-person DBT groups.

Time for completion: 5-10 minutes

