***Total time for Completion of above surveys: 20-30 minutes/assessment***

To minimize survey fatigue, only individuals who endorse difficulty with the following items will be asked to complete the questionnaires listed below at each assessment time point.

g. **Anger/Frustration** measured using the LEVEL 2 – Anger – Adult (PROMIS Emotional Distress – Anger - Short Form). This 5-item self-reported survey measures the pure domain of anger over the past 7 days, using a 5-point Likert scale ranging from 1 (never) to 5 (always).

Time for completion: 5 minutes

h. **Pain** using the PROMIS V1.1 - Pain Interference 6a Short Form. This 6-item self-reported survey measures the severity of pain and its impact on a person's ability to function over the past 7 days, using a 5-point Likert scale ranging from 5 (never) to 1 (always).

Time for completion: 5 minutes

i. **Sleep quality** using the LEVEL 2 – Sleep Disturbance – Adult (PROMIS Sleep Disturbance – Short Form). This 7-item self-reported survey measures sleep quality, sleep depth, and restoration, including difficulties with falling asleep or staying asleep and satisfaction with sleep over the past 7 days, using a 5-point Likert scale ranging from 1 (not at all) to 5 (very much).

Time for completion: 5 minutes

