### **Anonymity, Confidentiality and Data Security**

All members of the research team will respect study participants' privacy and confidentiality throughout the study. Measures will be taken to ensure that all the data collected for this study will remain confidential in accordance with privacy legislation. Study personnel will not transmit documents, other than that previously specified, or samples containing personal health identifiers (PHI) at any time over the course of the study. Each participant will be assigned a unique code and these numbers rather than names will be used to collect, store, and report participant information. Full names and other identifying information will not be revealed unless required by law and/or for the applicable REB review, or for auditing purposes. The Subject Identification Code List (i.e. participant key) that links the identity of the participant with subject ID for de-identified data will be maintained with the trial master file. The master file will be maintained both in electronic and hard copy format. The electronic file will be encrypted and stored on a dedicated research server that only the PI and study research staff will have access to. The identity of the participants will not be revealed in any published data or in presentation of the information obtained as a result of this study. Findings will be reported in aggregate.

Anonymity and confidentiality will be maintained as much as possible for PSP, DBT pilot intervention and focus group participants but cannot be guaranteed due to the nature of group participation. Ground rules will be established and reviewed at the beginning and end of the PSP workshop, each DBT session and focus group emphasizing the confidentiality of information shared within the group. Taking these precautions will assist in maintaining confidentiality of the data collected. Audio recordings and questionnaires will be stored in a locked filing cabinet in a locked office at the University of Manitoba for a period of 10 years after study completion and will then be destroyed. Electronic data including the study participant key and transcripts of audio files will be

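### The DBT pilot scores anxiety and distress three times in people enrolled for distress, but nothing links a very high score to a clinician

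*Protocol*

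**What the plan says.** All references are to the Protocol.

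- **Who is enrolled.** The inclusion criteria (Study Population, under Study Setting) require "Experiencing self-reported psychological distress related to advanced kidney disease or initiation of hemodialysis". The study psychologist must also judge each person eligible. The exclusions include "Requiring referral for psychiatric care as per facility-based HD care provider assessment".
- **What is measured.** Under Outcomes, all participants complete the 7-item PROMIS anxiety form and the Distress Thermometer, a single item running from 0 to 10 with extreme distress at the top. Table 2 schedules both at baseline, week 6 and week 12.
- **Where the forms go.** DBT Data Collection has the research coordinator distribute the surveys on paper or by email under a study identifier. Data management has a research assistant enter data into REDCap. DBT Statistical Analysis summarises and compares the scores in aggregate.
- **What an answer can trigger.** For anger, pain and sleep, "only individuals who endorse difficulty with the following items will be asked to complete the questionnaires listed below at each assessment time point". No other answer-driven step is described.
- **Who looks after well-being.** Risks and Benefits of Study Participation states that "external to research, the kidney care staff (social workers and nephrologists) will manage the well-being of clients through standard clinical care processes". It adds a resource list that includes renal social workers, an elder and a crisis line, which is supplied to participants, given to those who withdraw, and given to everyone again at the end of the program.
- **Confidentiality.** "Full names and other identifying information will not be revealed unless required by law and/or for the applicable REB review, or for auditing purposes". The file holding the participant key is "stored on a dedicated research server that only the PI and study research staff will have access to".

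**The concern.** A study that selects people for distress and then asks them three times how distressed and anxious they are will hold information that a clinician might want to act on. As written, an extreme answer is coded, entered and analysed in aggregate, and nobody on the study is asked to look at it as it comes in. The kidney staff who are responsible for well-being stand outside the research and are not stated to see it.

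What is at stake is timely use of information that the study already has. The people for whom this counts most are those whom the psychologist may not be seeing: participants who have stopped coming to sessions, and participants whose final form arrives after the last session.

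**Working it through.** The plan gives no figure to reproduce. The check is a reading of every DBT section, followed by a simple count for scale.

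**1. Can a score influence eligibility?** Table 2 places "FINAL STUDY ELIGIBILITY" at Visit 0. The first questionnaires are at Visit 1. On that schedule, no score is available when the exclusion for needing psychiatric referral is applied, and no later step in the schedule revisits that need.

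**2. Is a score reviewed after it is returned?** The stated steps are distribution by the coordinator, coding, data entry and aggregate analysis. None names a reviewer, a threshold, a time limit or a recipient. The branching to the anger, pain and sleep forms shows that an answer can trigger a step, but that step is another questionnaire.

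**3. Would a clinician see the person anyway?** Often, yes. The Intervention section has participants attend an orientation with the psychologist, then weekly sessions led by that psychologist. Individual check-ins are permitted but optional. Two situations weaken this contact:

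- *Non-attendance.* The feasibility target for mean attendance is at least 50%, that is 0.50 × 12 = 6 of 12 sessions. Missing 4 or more in a row is itself a counted outcome. The plan therefore expects some people to be out of the psychologist's sight when a form is due.
- *The week-12 form.* The assessment window is 10 days either side of the timepoint, so a form can come back up to 10 days after the program ends, when weekly contact has stopped.

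**4. Scale.** Inputs from Recruitment and Consent for DBT Groups are 15 in-person and 20 virtual participants. Table 2 gives 3 assessments.

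| Quantity | Calculation | Result |
|---|---|---|
| Participants, Manitoba | 15 + 20 | 35 |
| Score sets, ceiling | 35 × 3 | 105 |
| Baseline sets | 35 × 1 | 35 |
| Post-baseline sets | 35 × 2 | 70 |
| Week-12 sets | 35 × 1 | 35 |

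Each set holds one anxiety score and one distress score. The counts assume full recruitment and no dropout or missed forms, so they are upper limits. Halifax is to run the same protocol but has no stated sample size and is left out.

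**5. Coordinator time for a check.** The minutes per set are an assumption: 5, with a range of 2 to 10.

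- 105 × 5 / 60 = 8.75 hours
- 105 × 2 / 60 = 3.5 hours
- 105 × 10 / 60 = 17.5 hours

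**The case against.** The strongest reply is that these participants are not without care. A psychologist judges each one eligible, meets them at orientation and leads the group every week. Everyone is enrolled for distress, so a raised baseline score largely repeats what is already known. People who miss DBT sessions are still on hemodialysis or about to start it, and are seen by the staff whom the plan makes responsible for their well-being. Relying on usual care plus a resource list is a deliberate choice, and the consent form, which is not shown, may say more. All of this stands, and it limits the point to the missing link between a score and a clinician. It does not supply that link.

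Several stronger readings are tempting but not supported:

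- *That non-attenders would never get the resource list.* The list goes to participants generally and to all of them again at the end; the copy at withdrawal is an extra.
- *That giving the final list before the week-12 form is a gap.* Having the contacts in hand beforehand is, if anything, protective.
- *That the workshop and focus groups have debriefing while the DBT questionnaires have none.* The risk section recognises discomfort from answering questions and offers social workers, an elder and a crisis line for debriefing as needed. Neither the workshop nor the focus groups review scores either.
- *That the confidentiality section forbids a hand-over.* Its listed exceptions do not mention one, so permission is unclear for kidney staff outside the study. The psychologist already has a role within the study, and a hand-over to that person is not clearly barred. The access limit quoted above concerns the file with the participant key, not the scores.
- *That serious harm is likely.* No suicidality item is described, and nothing in the Protocol allows a count of high scores.

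**Conclusion.** The point holds in a limited form. The Protocol collects up to 105 sets of anxiety and distress scores in Manitoba from people enrolled for distress, and states no step by which a very high score reaches a clinician. Existing safeguards are real, but a score triggers none of them. The exposure is concentrated in participants who have stopped attending and in the week-12 forms, at most 35, that may come back after the last session.

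This rests on the Protocol text alone, on full enrolment for the counts, and on the unseen consent form not already setting up such a step. Consent wording by itself would still not assign a reviewer. A participant-safety procedure of this kind belongs in the protocol, not in a statistical analysis plan. It is a cheap improvement, held with medium confidence.

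**What to change.** Amend three sections.

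- **DBT Data Collection and Risks and Benefits of Study Participation.** The coordinator checks the Distress Thermometer and PROMIS anxiety form at baseline, week 6 and week 12 within a fixed short time of return, for example 2 working days. Any score at or above a cut-off goes to the study psychologist, who sets that cut-off before the first group, high enough to stand out in people already enrolled for distress. If the participant has stopped attending or the program has ended, it goes to the renal social worker at the participant's own site. The site matters because the resource list names only SOGH social workers, while the virtual group also recruits from HSC. What care follows is left to the clinicians.
- **Anonymity, Confidentiality and Data Security.** State that this hand-over to the clinical team is permitted, and add it to the consent form if it is not already covered. The participant key held by the research team makes it workable.
- **Reporting.** Record each hand-over and report the number per timepoint beside the secondary outcomes.

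The cost is one amendment, about 9 coordinator hours (3.5 to 17.5 under the assumed range), and some psychologist and social-worker time that cannot be sized without knowing how many scores exceed the cut-off. Participants might under-report distress slightly if they know that scores are passed on. A hand-over is a minor co-intervention on the uncontrolled pre/post changes, which is why it should be counted. Contacting people who have stopped attending could also have a small effect on attendance or withdrawal, which are primary feasibility outcomes.
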